### 3.2.3 Additional Evaluation of Efficacy

The additional efficacy evaluations in this study are:

- Hb Maintenance:
  - Hemoglobin Long-Term Maintenance: Mean change from BL in Hb averaged over 8 weeks of treatment at Weeks 44 to 52 without rescue therapy within 6 weeks prior to and during this 8-week evaluation period
  - Mean change from BL in Hb averaged over the final 8 weeks of treatment, without rescue therapy within 6 weeks prior to and during this 8-week evaluation period
  - Change from BL in Hb at each of the selected postdosing time points
  - Proportion of subjects with 10-12 g/dL averaged over Weeks 28 to 36, 44 to 52, and the final 8-weeks of treatment without rescue therapy within 6 weeks prior to and during this 8-week evaluation period
  - Hb response during Weeks 28 and 36 regardless of use of rescue therapy
  - Hb change from BL to the average Hb value of Weeks 28 to 36, 44 to 52, and the final 8 weeks of treatment regardless of the use of rescue therapy
- Iron Supplement:
  - Requirement for IV iron supplementation
  - Mean monthly IV iron (mg) per subject during Weeks 37 to 52 and Week 53 to EOS
  - Mean monthly oral iron (mg) use per subject during Weeks 1 to 36, Weeks 37 to 52, and Weeks 53 to EOS
  - Requirement for only oral iron supplementation
- Hospitalizations:
  - Occurrence (number) of hospitalizations
  - Proportion of subjects hospitalized
  - Number of days of hospitalizations per patient-exposure year (PEY)

- Missed Dialysis:
  - Occurrence (number) of missed dialysis sessions
  - Proportion of subjects with missed dialysis sessions
  - Number of days of missed dialysis sessions per patient-exposure year (PEY)
- Rescue Therapy Use:
  - Proportion of subjects who receive RBC transfusions
  - Number of RBC packs per patient-month exposure to study medication
  - Having received rescue therapy [composite of RBC transfusions and rescue ESA]
- Changes in Cholesterol Levels:
  - Change from BL at each of the selected treatment time points in:
    - Total cholesterol
    - Low-density lipoprotein/high-density lipoprotein ratio
    - Non-HDL cholesterol
  - Proportion of subjects achieving LDL target of < 100 mg/dL averaged over Weeks 12 to 28 of treatment
- Blood Pressure Effect:
  - Proportion of subjects achieving BP treatment goal in ESRD subjects (predialysis systolic BP < 140 mmHg and diastolic BP < 90 mmHg) averaged over Weeks 12 to 28
  - Time to a treatment-emergent AE of hypertension

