## 4 STUDY DESIGN

### 4.1 Description of the Study

This open-label, randomized, active controlled study is designed to evaluate the efficacy and safety of roxadustat compared to epoetin alfa for the maintenance of hemoglobin (Hb) levels in subjects on HD or PD or HHD originally on ESA for treatment of anemia.

- **Screening Period:** Up to 6 weeks. For subjects currently taking Mircer®, the Screening Period can be extended up to 8 weeks
- **Treatment Period:** Treatment duration is variable for individual subjects, with a minimum treatment duration of 52 weeks and a maximum duration of up to approximately 3 years after the last subject is randomized

**Amendment 1& 2:** In order to complete the Phase 3 program in a timely manner, minimum treatment duration of subjects enrolled under Amendment 1 & 2 may be shortened. Subjects will be informed at least 4 weeks in advance if such decision is made. All active subjects will end the study at the same time

- **Post-Treatment Follow-Up Period:** 4 weeks

During the course of the study, visits and assessments will be performed as defined in the schedule of assessments.

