4.3 Additional Evaluation of Efficacy

The additional efficacy evaluations in this study are:

- **Hemoglobin Maintenance:**
 - Hemoglobin long-term Maintenance: Mean change from baseline in hemoglobin averaged over 8 weeks of treatment at Weeks 44-52 without

- rescue therapy within 6 weeks prior to and during this 8-week evaluation period.
- Mean change from baseline in hemoglobin averaged over the Week 96 to 104 of treatment, without rescue therapy within 6 weeks prior to and during this 8-week evaluation period.
 - Change from baseline in hemoglobin at each of the selected post-dosing time points.
 - Proportion of subjects with Hb ≥ 10 g/dL averaged over Weeks 28 to 36, 44 to 52, and 96 to 104 of treatment without rescue therapy within 6 weeks prior to and during the evaluation periods.
 - Proportion of subjects with Hb ≥ 10 g/dL averaged over Weeks 28 to 36, 44 to 52, and 96 to 104 of treatment regardless of rescue therapy
 - Proportion of subjects with Hb within 10-12 g/dL averaged over Weeks 28 to 36, 44 to 52, and 96 to 104 of treatment without rescue therapy within 6 weeks prior to and during these 8-week evaluation periods.
 - Proportion of subjects with Hb within 10-12 g/dL averaged over Weeks 28 to 36, 44 to 52, and 96 to 104 of treatment regardless of rescue therapy use.
 - Hemoglobin change from baseline to the average hemoglobin value of weeks 28 to 36, 44 to 52, and 96 to 104 of treatment regardless of the use of rescue therapy.
- **Iron Supplement:**
 - Time to and Proportion of subjects who has requirement for IV iron supplementation.
 - Mean monthly IV iron (mg) per subject during weeks 28-52, 53-104, and 105 -EOT.
 - Mean monthly oral iron (mg) use per subject during 28-52, 53-104, and 105 - EOT.
 - Proportion of subjects who has Requirement for only oral iron supplementation (Week 1 to 52).
 - **Hospitalizations**
 - Time to first hospitalization (% of subjects) up to Week 52, 7 days after Last Dose. Time to first hospitalization or skilled nursing facility (% of subjects) up to Week 52, 7 days after Last Dose.
 - Number of days of hospitalizations due to AE per subject-exposure year (PEY)
 - Number of days in hospital or skilled nursing facility due to AE per patient-year exposure (PEY)
 - Number of days in medical-facility (hospital, skilled nursing facility, emergency room, or overnight observation) due to AE per patient-year exposure (PEY)

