11.3 Additional Efficacy Analyses

11.3.1 Hemoglobin Maintenance

11.3.1.1 Hemoglobin long-term Maintenance

Hemoglobin long-term maintenance will be assessed by:

- Mean change in hemoglobin averaged over 8 weeks of treatment at Weeks 44-52 without rescue therapy within 6 weeks prior to and during this 8-week evaluation period.
- Mean change in hemoglobin averaged over the Week 96- 104 of treatment without rescue therapy within 6 weeks prior to and during this 8-week evaluation period.
- Change in hemoglobin at each of the selected post-dosing time points
- Proportion of subjects with hemoglobin ≥ 10 g/dL averaged over 36 to 44, 44 to 52, and the Week 96- 104 without rescue therapy within 6 weeks prior to and during this 8-week evaluation period.
- Proportion of subjects with hemoglobin within 10-12 g/dL averaged over 36 to 44, 44 to 52, and the Week 96- 104 without rescue therapy within 6 weeks prior to and during this 8-week evaluation period.
- Hb response during Weeks 28 and 36 regardless of use of rescue therapy
- Hb change from BL to the average Hb value of Weeks 28 to 36, 44 to 52, and 96 to 104 of treatment regardless of the use of rescue therapy

The change in hemoglobin, will be analyzed using MMRM model with baseline hemoglobin as a covariate, treatment group, visit, the interaction of treatment and visit, and stratification factors except mean qualifying screening hemoglobin (≤ 10.5 vs. >10.5 g/dL) as factors.. The same strategy as that used in MMRM in Section 11.1.2.1 will be used to choose variance covariance. Data up to visit of Week 52 will be included in the analyses. The estimates for

the difference of change from baseline in Hemoglobin for Week 28 to 36 and 44 to 52 between the two treatment groups will be generated from an estimate statement. The mean change in Hb averaged over 8 weeks of treatment at Weeks 96-104 will be analyzed using the MI analyses as the one for the primary efficacy endpoint of US-submission.

The proportion of subjects with hemoglobin within 10-11 g/dL in US and 10-12 g/dL in Ex-US will be analyzed using logistic regression model including baseline hemoglobin as a covariate and treatment group and stratification factors except mean qualifying screening hemoglobin (≤ 10.5 vs. >10.5 g/dL) as fixed effects.

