Hemoglobin change from baseline to the average hemoglobin value of the Week 96 to 104 weeks of treatment will be analyzed using an MI ANCOVA model with baseline hemoglobin as a covariate, and treatment group and stratification factors except mean qualifying screening hemoglobin (≤ 10.5 vs. >10.5 g/dL) as fixed effects, using the Hb mean from the non-missing weeks.

In this study, there are patients in whom roxadustat dose frequency needed to be reduced to BIW or QW as part of their dose reduction below the lowest possible TIW dose of 20 mg TIW during treatment, to evaluate Hb maintenance, the following summary will be provided for these subgroups of subjects treated on BIW or QW (including any frequency $<QW$) for longer than 8 weeks (i.e., ≥ 56 days):

- Average Hb values over time for every 4-8 weeks after the initiation of BIW or QW
- Average weekly dose over time for every 4-8 weeks after the initiation of BIW or QW

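### The SAP moves the long-term hemoglobin endpoints from the final eight weeks of treatment to Weeks 96–104 without flagging it, and gives two averaging rules for the change endpoint that cannot both be followed

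*SAP*

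**What the plan says.** Protocol 3.2.3 sets three hemoglobin-maintenance evaluations at the end of each subject's own treatment:

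- a change without rescue: "Mean change from BL in Hb averaged over the final 8 weeks of treatment"
- a proportion within 10–12 g/dL: "44 to 52, and the final 8-weeks of treatment without rescue therapy"
- a change whatever the rescue use: "44 to 52, and the final 8 weeks of treatment regardless of the use of rescue therapy"

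SAP 4.3 keeps the three evaluations but fixes the last window in study time, as "Mean change from baseline in hemoglobin averaged over the Week 96 to 104 of treatment" and "44 to 52, and 96 to 104 of treatment regardless of the use of rescue therapy", and does the same for the 10–12 g/dL proportion. It also adds proportions at or above 10 g/dL over Weeks 96–104.

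Treatment length varies by subject, "with a minimum treatment duration of 52 weeks and a maximum duration of up to approximately 3 years after the last subject is randomized" (Protocol 4.1). The same section allows the minimum to be shortened for subjects enrolled under Amendments 1 and 2. Protocol 4.1.2 adds an event-driven closeout common to all subjects.

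SAP 11.3.1.1 has two sentences on the Weeks 96–104 change. The first says that it "will be analyzed using the MI analyses as the one for the primary efficacy endpoint of US-submission". The second, two paragraphs later, calls for an ANCOVA with multiple imputation, "using the Hb mean from the non-missing weeks".

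Protocol 9.6 says that significant changes to the protocol's analyses will be highlighted in the SAP.

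**The concern.** The two windows do not cover the same subjects. The protocol's window moves with the subject, so anyone treated for about eight weeks or more can contribute. The SAP's window exists only for subjects still on treatment near two years. Some subjects may never be scheduled to get there, and the SAP does not separate them from those who drop out. The protocol's summary is not produced anywhere in the SAP text, and the replacement is not marked as a change.

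The two sentences in 11.3.1.1 leave the computation open. If every gap is imputed, all analysed subjects contribute. If only non-missing weeks are averaged, subjects without a value in the window have no outcome. In an open-label trial that choice should not be left until the data are in hand. At stake is how the long-term maintenance result is read, not the primary conclusion.

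**Working it through.** **The plan's own figure.** The only design figure nearby is the power in SAP 5.1. With 300 per arm, an assumed difference of −0.30 g/dL, a margin of 0.75, an SD of 1.25 and two-sided 5%:

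- distance to the margin = 0.75 − 0.30 = 0.45
- standard error = 1.25 × √(2/300) = 0.102
- 0.45/0.102 = 4.41, and 4.41 − 1.96 = 2.45, giving power 0.993

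The stated figure of at least 99% is reproduced. It does not depend on the Weeks 96–104 endpoints.

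**Windows side by side.**

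| Evaluation | Protocol 3.2.3 | SAP 4.3 |
|---|---|---|
| Change, without rescue | subject's last 8 weeks | Weeks 96–104 |
| Proportion 10–12 g/dL, without rescue | subject's last 8 weeks | Weeks 96–104 |
| Change, regardless of rescue | subject's last 8 weeks | Weeks 96–104 |

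**Can treatment end before the window by design?** SAP Appendix 5 puts scheduled visits at Day 7 × week + 1. The window signs in Table 11 are garbled in the text; I read them as −14 to +13 days from Week 28 onward.

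- Week 96: 7 × 96 + 1 = Day 673, window Days 659–686
- Week 104: 7 × 104 + 1 = Day 729, window Days 715–742
- Minimum planned treatment: 52 × 7 = 364, so the last day is Day 364
- Gap to the opening of the Week 96 window: 659 − 364 = 295 days

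This subject can be evaluated under the protocol's window and has no data in the SAP's.

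**Each averaging rule applied to that subject.** Visits are four-weekly after Week 24.

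- *First sentence.* The US primary method (SAP 11.1.1.1) imputes to the end of the evaluation period and averages values whether observed or filled in. It would impute (104 − 56)/4 + 1 = 13 consecutive visits, Weeks 56 to 104, including all three in the window (96, 100, 104). The subject contributes a value.
- *Second sentence.* The mean is over non-missing weeks. None of Weeks 96, 100 and 104 is observed, so there is nothing to average. Read instead as applying after imputation, the clause has no effect, because no week is then missing. The clause therefore conflicts with the first sentence or is redundant under its own model.

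**How many subjects?** The documents do not say. Let f be the share whose treatment ends by design before Week 96. Assuming f = 10%, 25% or 50%, of 600 randomized subjects 600 × (1 − f) = 540, 450 or 300 could supply observed values, before any dropout. If closeout came about three years (3 × 52 = 156 weeks) after the last randomization, every subject's planned treatment would pass Week 104 and f would be zero.

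**The case against.** A fixed window has merit. It compares the arms at the same time on treatment, whereas a final-eight-weeks window mixes subjects who stopped after a few months with subjects treated for years. Protocol 9.4.3.2 leaves methods for additional endpoints to the SAP. Closeout is common to both arms, so administrative truncation alone has no evident reason to favour either. These points stand: Weeks 96–104 need not be withdrawn, and no between-arm bias has been shown.

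It can also be said that both sentences are labelled multiple imputation and that they may serve different endpoints, one without rescue and one regardless of it. Neither sentence says so. The US primary imputation does not censor values influenced by rescue (SAP 11.1.1.1), so giving the first sentence to the without-rescue endpoint would put a rescue-inclusive method on it. The conflict remains, though it is one of wording.

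A reader might infer more than the documents support:

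- *That the Weeks 96–104 proportions are rates among completers and overstate durable control.* The SAP does not say that subjects without a value are dropped; it is silent, as it is for the earlier windows in the same bullets. The logistic model in 11.3.1.1 is stated for 10–11 g/dL (US) and 10–12 g/dL (Ex-US), not for the proportions at or above 10 g/dL.
- *That the approximately 150 amendment subjects (150/1200 = 12.5% to 150/600 = 25%) are certain to miss the window.* Protocol 4.1 says only that their minimum may be shortened. Under Protocol 9.3 they also do not enter the EU efficacy analyses.
- *That everyone off drug before Week 96 should count as a failure.* Neither document sets that rule for these endpoints. Protocol 5.3 lists death and kidney transplant among the discontinuation reasons, so such a rule would count both as hemoglobin failures.

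**Conclusion.** The point holds as an unflagged change of endpoint and a contradictory computing rule. Three protocol evaluations have a different window in the SAP, and the SAP text available for review does not mark the change; whether it counts as significant under Protocol 9.6 is a judgement, but it changes who can be evaluated. The second averaging sentence cannot be followed together with the first, and read literally it cannot be computed for a subject with no hemoglobin value in the window.

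The size is limited. These are additional endpoints outside the fixed testing sequence (SAP 11.2.1, Table 6), and maintenance is still reported over Weeks 28–36 and 44–52. The number affected ranges from none by design under a late closeout to a substantial share under an early one, and the documents do not fix the closeout date. The 295-day gap rests on a subject treated for exactly the 52-week minimum and on the −14/+13 reading of Table 11. A somewhat different window width would not change the conclusion, because Week 96 itself is 44 weeks beyond the minimum.

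**What to change.** 1. In SAP 11.3.1.1, delete the clause on non-missing weeks, so that the US primary multiple imputation is the single rule for the Weeks 96–104 change, with Week 104 as the end of the evaluation period. For the without-rescue version, say whether rescue-influenced values are set to missing first; SAP Table 5 already has such a variant for the US endpoint.
2. Flag in the SAP that Weeks 96–104 replaces the protocol's window, with the reason, and report the protocol's final-eight-weeks summary alongside it.
3. For the Weeks 96–104 proportions, report by arm the number with the opportunity to reach Week 104, given randomization and closeout dates, and use it as the denominator. Show how many of them have no hemoglobin value in the window and state in advance how they are handled. The choice of rule is the sponsor's.

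The cost is SAP wording and one or two extra derivations from hemoglobin values and dates already collected. No new data are needed, and sample size and alpha do not change.

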### **5.3 Subject Discontinuation and Withdrawal**

The subject is free to permanently discontinue study medication at any time, without prejudice to further treatment. Discontinuation from study medication is not the same as complete withdrawal from the study (ie, withdrawal of consent).

Subjects may withdraw consent and discontinue from the study at any time by discontinuing study medication and refusing to return for any form of follow-up without any prejudice.

A subject who decides to discontinue study medication will always be asked about the reason(s) to discontinue study medication and the presence of AEs (if any). These data will be ascertained and documented by the investigator and recorded in the eCRF as appropriate. The subject should return all study medications.

Reasons for permanent discontinuation of study medication:

- Subject's decision (subject no longer wants to continue study medication (ie, withdrawal of consent))
- Investigator's decision that it is in the best interest of the subject to be withdrawn from the study
- Adverse events
- Significant noncompliance with study procedures, as determined by Investigator or Sponsor
- Lack of efficacy / Meets ESA withdrawal criteria
- Subject is lost to follow-up
- Subject is no longer requiring dialysis due to kidney transplant
- Site terminated by the sponsor

- Pregnancy
- Death

Upon discontinuation from the study, both female subjects of childbearing potential and male subjects with partners of childbearing potential must continue to use a medically acceptable method of contraception for 12 weeks following the last study drug administration.

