During the Treatment Period, subjects will attend weekly study visits from Day 1 to Week 2, followed by every two weeks study visits from Weeks 4 to 24. Following Week 24, study visits will occur every four weeks until the End of Treatment (EOT). After EOT, subjects proceed to the post-treatment Follow-up Period and will return for the End of Study (EOS) visit. The schedule of assessments for the study is provided in Appendix 1.

All subjects discontinuing study medication prematurely will be followed up for vital status, cardiovascular events, and hospitalization until study closure, unless consent to participate is withdrawn. Upon completion of ET and 4-week Follow-up (EOS) visits, these subjects will be followed up every 3-6 month interval (depending on the availability of subjects) until study closure. These visits may occur either in-person or via telephone.

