3.2 Rescue Therapy & Emergency Procedures

Red Blood Cell Transfusion (for all subjects):

For subjects in both treatment groups, red blood cell (RBC) transfusion is allowed if rapid correction of anemia is required to stabilize the subject's condition (e.g. acute hemorrhage) or the investigator is of the opinion that the blood transfusion is a medical necessity. Study treatment may continue during or after RBC transfusion administration.

ESA use:

For subjects randomized to roxadustat the use of ESAs is generally prohibited. ESA rescue is restricted to no more than one 4-week cycle of use during the Treatment Period; the Investigator may initiate use of an approved epoetin (EPO) analogue if all of the following criteria are met:

- A subject's hemoglobin level has not sufficiently responded to two or more dose increases or the maximum dose limit of the study drug has been reached; and
- The subject's hemoglobin is < 8.5 g/dL on two consecutive measurements (central lab) drawn at least five days apart; and
- Clinical judgment does not suggest iron deficiency or bleeding as a cause of lack of response or rapid decline in hemoglobin; and
- Reducing the risk of alloimmunization in transplant eligible patients and/or reduction of other RBC transfusion-related risks is a goal

The subject is not allowed to be administered both the EPO analogue and roxadustat at the same time. Treatment with an EPO analogue should be started ≥ 3 days after the last dose of roxadustat, and should be stopped when hemoglobin > 9 g/dL or after a 4-week cycle has been completed, whichever comes first. If a subject requires longer than 4-week therapy due to inadequate response, the Medical Monitor should be contacted. Study treatment should be resumed after the following intervals:

- Two days after stopping epoetin
- One week after stopping darbepoetin alfa
- Two weeks after stopping methoxy polyethylene glycol-epoetin beta (Mircera[®])

If more than one cycle of EPO analogue rescue is required, the Investigator should permanently discontinue roxadustat. Use of EPO analogues will be recorded in the eCRF. Roxadustat subject who receives an ESA inadvertently and does not meet the criteria above may be allowed to continue taking study medication, if considered safe by the Investigator or Medical Monitor.

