 - Hospitalization-free survival days on treatment up to Week 52, 7 days after Last Dose. The days will be compared between the 2 treatment groups using ANCOVA model with baseline Hb and the baseline stratification factors.
 - Number of days on treatment out of hospital and skilled nursing facility up to Week 52, 7 days after Last Dose. Similar analysis as above will be performed.

- **Missed Dialysis:**
 - Occurrence (number) of missed dialysis sessions per subject.
 - Proportion of subjects with missed dialysis sessions.
 - Number of days of missed dialysis sessions per patient-exposure year (PEY).
- **Rescue Therapy Use:**
 - Proportion of subjects who receive RBC/blood transfusions.
 - Number of RBC/blood packs per subject-month exposure to study medication.
 - Proportion of subjects who received rescue therapy [composite of RBC transfusions and/or rescue ESA].
 - Time to initial rescue therapy.
- **Changes in Cholesterol Levels:**
 - Change from baseline at each of the selected treatment time points (Weeks 12-28, every 8 weeks onward until Week 52) in:
 - total cholesterol,
 - low-density lipoprotein/high-density lipoprotein ratio,
 - Non-HDL cholesterol.
 - Proportion of subjects achieving LDL target of <100 mg/dL averaged over Weeks 12-28 of treatment for subjects whose baseline LDL \geq 100.
- **Blood Pressure Effect:**
 - Proportion of subjects achieving blood pressure treatment goal in ESRD subjects (predialysis systolic BP <140 mmHg and diastolic BP <90 mmHg) averaged over Weeks 12-28.
 - Time to first exacerbation of hypertension from baseline during weeks 1 to 36 defined as:
 - An increase from baseline of \geq 20 mmHg systolic BP (SBP) and SBP >170 mmHg
 - Or,
 - An increase from baseline of \geq 15 mmHg diastolic BP (DBP) and DBP >100 mmHg
 - Time to a treatment-emergent AE of hypertension.
 - Time to exacerbation from baseline of antihypertensive therapy.
 - Proportion of subjects with exacerbation of hypertension, defined as an increase from baseline of \geq 20 mmHg systolic BP and sBP >170 mmHg or an increase from baseline of \geq 15 mmHg diastolic BP and dBP >100 mmHg.
 - Proportion of subjects with a treatment-emergent AE of hypertension.
 - Proportion of subjects with exacerbation from baseline of antihypertensive therapy.
- **Vascular Access Thrombosis (HD subjects):**
 - Time to a treatment-emergent AE of vascular access thrombosis
 - Proportion subjects with a treatment-emergent AE of vascular access thrombosis

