11.3.2 Hospitalizations

Hospitalizations are collected in the Hospitalization Records Form of the eCRF. For each subject, an entry will be recorded for each hospitalization. The days of hospitalization will be calculated as the sum of all hospitalizations durations in days (Date of discharge – Date of Admission + 1). In case of missing dates, the hospitalization duration will be assumed to be 5 days.

Only hospitalizations with admission dates that occur during the Treatment Period and up to 7 days after the last study medication date will be taken into account.

The following hospitalization-related data will be analyzed and compared between the 2 treatment groups:

- Time to first hospitalization (% of subjects) up to Week 52, 7 days after last dose.
- Time to first hospitalization or skilled nursing facility (% of subjects) up to Week 52, 7 days after last dose.
- Number of days of hospitalizations
- Number of days of medical-facility
- Number of days of hospitalizations per patient-exposure year (PEY).
- Number of days in hospital or skilled nursing facility per patient-year exposure (PEY).
- Number of days of medical-facility (hospital, skilled nursing facility, emergency room, or overnight observation) per subject-exposure year (PEY).
- Number of days on treatment out of hospital and skilled nursing facility up to Week 52, 7 days after Last Dose.

Note: Sensitivity analysis may be performed by excluding elective procedures using only hospitalization due to AE

The time to hospitalization event will be compared between the two treatment groups using cox model including baseline stratification factors. The proportion of subjects hospitalized will be compared between the 2 treatment groups using logistic regression model and stratified by the baseline stratification factors. The mean number of days of hospitalization will be analyzed and compared between the 2 treatment groups using the Mantel-Haenszel mean score test adjusting for stratification factors.

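### Hospitalization-free days are compared as raw on-treatment totals, so unequal drug discontinuation can create an arm difference when survival and hospitalization are identical

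*SAP*

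**What the plan says.** SAP 4.3, under Hospitalizations, lists "Hospitalization-free survival days on treatment up to Week 52, 7 days after Last Dose". The analysis follows directly: "The days will be compared between the 2 treatment groups using ANCOVA model with baseline Hb and the baseline stratification factors". The next item is "Number of days on treatment out of hospital and skilled nursing facility up to Week 52, 7 days after Last Dose", to be analysed in a similar way.

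SAP 11.3.2 repeats the second of these endpoints but not the first, and gives a formula for neither. It limits the admissions that count: "Only hospitalizations with admission dates that occur during the Treatment Period and up to 7 days after the last study medication date". The one sensitivity analysis it names is "Sensitivity analysis may be performed by excluding elective procedures using only hospitalization due to AE", which leaves the counting window untouched.

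The other hospital-day measures in SAP 4.3 are expressed per exposure year. These two are not. Protocol 3.2.3 lists neither; both were added in the SAP.

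On follow-up after stopping drug, SAP 3 says: "All subjects discontinuing study medication prematurely will be followed up for vital status, cardiovascular events, and hospitalization until study closure". This lapses if consent is withdrawn, and the contacts, every 3 to 6 months in person or by telephone, depend on subjects being available. Protocol 4.1.4 and 7.2.2 agree. Skilled nursing stays are not among the items collected in that follow-up.

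**The concern.** An endpoint with survival in its name will be read as a clinical outcome. Under a day count capped at last dose + 7 days, time off drug scores zero, just as time dead or in hospital does. Reasons for stopping drug include outcomes that are not failures of treatment; Protocol 5.3 lists "Subject is no longer requiring dialysis due to kidney transplant".

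The arms could well stop drug at different rates. The trial is open-label, and one stopping rule applies to roxadustat only: "If more than one cycle of EPO analogue rescue is required, the Investigator should permanently discontinue roxadustat". In the epoetin arm SAP 3.2 allows a different EPO analogue and states no matching stop rule. A nominally significant difference in days could then be taken as benefit or harm when it reflects persistence on drug.

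**Working it through.** **The plan's own figure.** No power or expected difference is stated for these endpoints. The only power figure concerns the primary non-inferiority test (SAP 5.1): difference −0.30, margin 0.75, SD 1.25, 600 subjects. With 300 per arm, (0.75 − 0.30) / (1.25 × √(2/300)) = 0.45 / 0.102 = 4.41, and Φ(4.41 − 1.96) = 99.3%. This reproduces the stated 99% but does not bear on the present point.

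**Scores for single subjects, day-count reading.**
- Stops drug at Week 10 and lives on: at most 70 + 7 = 77 days.
- Stops at Week 12, survives, is never admitted: 84 + 7 = 91 days.
- Dies on drug at Week 40 without an admission: about 280 days.
- Stays on drug to Week 52 with 20 hospital days: 364 − 20 = 344 days.

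**Rough size by hand.** Assume uniform stopping times and ignore deaths and admissions. A stopper then loses on average about 364/2 − 7 = 175 countable days. A gap of 10 percentage points gives 0.10 × 175 = 17.5 days; 5 points give 8.75; 15 points give 26.25.

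**Simulation.** 100,000 subjects per arm. Death and hospitalization have the same distribution in both arms and are independent of stopping drug; only the 52-week stopping rate differs. Assumed ranges: 5–15% deaths by Week 52, 0.5–1.7 admissions per year, mean stay 7 days. Score = days alive and out of hospital up to the earliest of last dose + 7, death and day 364. Rejection is a two-sided 5% two-sample test at the plan's sizes, 600 to 1200 subjects randomized 1:1.

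| Stopped by Week 52 | Difference (days) | Rejection, N=600 | Rejection, N=1200 |
|---|---|---|---|
| 20% vs 20% | about 0 | 5% | 5% |
| 25% vs 20% | −8 to −10 | 14–23% | 23–41% |
| 30% vs 20% | −16 to −19 | 45–64% | 74–90% |
| 35% vs 20% | −26 to −28 | 81–92% | 98–100% |

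One cell by formula (1.0 admission per year, 10% deaths, 30% vs 20%): difference 18.2, SD 104.8.
- N=600: 18.2 / (104.8 × √(2/300)) = 18.2 / 8.56 = 2.13; Φ(2.13 − 1.96) = 57%.
- N=1200: 18.2 / (104.8 × √(2/600)) = 18.2 / 6.05 = 3.01; Φ(3.01 − 1.96) = 85%.

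Time on drug explains 53–86% of the variance of this score, while hospital days average only about 3–11 per subject.

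**Other reading of the first endpoint.** If it means days to first hospitalization or death with the same cap, 30% vs 20% gives −8 to −14 days, with rejection of 12–25% (N=600) and 19–45% (N=1200). Time on drug then explains 9–37% of the variance.

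**Counting to Week 52 or death whatever the drug status.** The arm difference is about 0 and rejection about 5% in every scenario, under either reading.

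**The case against.** An on-treatment summary is a legitimate supportive choice. Anemia treatment after stopping is left to the investigator, both endpoints are openly labelled as on treatment, and the window matches the efficacy period in SAP 11. Hospital days per exposure year and time to first hospitalization are reported alongside, and the Kaplan-Meier plots of discontinuation in SAP 6 would expose a persistence gap. All of this stands, and it limits the harm. It does not rescue an unscaled total: an on-treatment count needs a denominator.

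The text is also incomplete. It does not say how the Week 52 limit and the 7-day limit combine, or how days after the cap are scored. A reader might infer that the first endpoint mainly measures time on drug. That holds for a day count, which the sibling's wording supports, but not for days to first event, where the bias keeps its direction and is smaller.

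A reader might also infer that data for a full Week 52 count exist for everyone and for both endpoints. The documents do not support that. Follow-up after stopping drug does not list skilled nursing stays, ends on withdrawal of consent, and depends on subjects being available.

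**Conclusion.** The defect is real and lies in the definition: raw totals, an on-treatment cap and no exposure term. Under the day-count reading, a 10-point gap in stopping moves the comparison by about 16–19 days with no difference in survival or hospitalization, and false rejection far exceeds 5%. The size rests wholly on assumed rates and on stopping being independent of hospitalization; with equal stopping there is no arm bias.

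It would be tempting to conclude that the trial will show a false difference, or that roxadustat will be the arm penalised. Neither follows. No discontinuation rates are given, and the bias runs against whichever arm stops drug more often.

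The consequence is limited. Both are additional endpoints outside the fixed sequence in SAP Table 6, and SAP 5.3 makes no multiplicity adjustment for them. The definitions should still be corrected, because a nominally significant result under this title is easily misread.

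**What to change.** 1. State the formula, window and population for both endpoints in SAP 11.3.2.
2. Define the hospitalization endpoint as days alive and out of hospital from first dose to Week 52, or to common closeout if earlier, regardless of study-drug status. Use the existing follow-up after discontinuation and score days after death as 0.
3. Add a rule for withdrawn consent and loss to follow-up, for example censoring or imputation. Unobserved days should not be scored as zero.
4. For the skilled nursing endpoint, keep the on-treatment window but analyse days per day at risk, with the denominator defined, instead of a raw total.
5. An on-treatment hospitalization version may stay as supportive, also per day at risk.

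The cost is SAP wording and programming, with no new data collection. Admission dates after stopping drug come from contacts 3 to 6 months apart and will be less exact, so the 5-day default for missing dates in SAP 11.3.2 may apply more often. Subjects enrolled under Amendments 1 and 2 may have shorter follow-up because of closeout; randomization should balance this between arms.
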